### **Primary time point definition**

The primary time point is defined as the average of Weeks 13 and 14. If the assessment is missing in one of the two time points, then non-missing assessment will be used.

### **End of treatment period assessment definition**

The end of treatment period assessments are defined as the last available assessments within 14 days after the last dose.

**Analytical visits:**

Efficacy/PD data including spirometry, CAT, SGRQ, sputum mucins, ENaC mRNA, inflammatory biomarkers, during the treatment period will be mapped to analysis visit as specified in the table (

**Efficacy/PD Measure Visit Windows**) below. The intent of these visit windows is not to align with those prescribed for visit scheduling in the clinical study protocol but, rather, based on the protocol-defined target study day, to delineate mutually exclusive windows so that all assessments proximal to a particular study week can be integrated to best represent the patient's status during that period of the study.

If a patient discontinued early from the treatment period but attended applicable landmark visits to collect assessments, then those assessments collected within 14 days after the last dose of Study Drug will be included as long as they are within the defined analysis windows.

The unscheduled visits will also be included if they are collected within 14 days after the last dose of Study Drug and within the defined analysis windows.

If there are multiple assessments within a visit window, the visit nearest the scheduled date will be used unless 2 visits are equally near, in which case the average will be used for continuous results, and the worst will be used for categorical results.

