### **3.4. Overall Study Duration and Follow-up**

The study will consist of Screening, Treatment, and Post-Treatment Periods. Please refer to the Schedule of Procedures in [Appendix A](#).

The study for an individual patient will generally consist of the following Periods:

- A  $\leq$  4-week Screening Period. The last week of which is the Run-in Period
- A 13-week Treatment Period during which study medication (ION-827359 or placebo) will be administered by nebulization once per week (both in-clinic and at home dosing)
- A 10-week Post-Treatment Period

Patients may be required to attend additional visits for monitoring of AEs or abnormal investigation results. The frequency of additional monitoring will be determined by the Study Medical Monitor in consultation with the Investigator.

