**Table 1: Withhold Time for Bronchodilators Prior to Study Visit:**

Bronchodilator	Withhold Time
SABA (e.g., albuterol or salbutamol)	6 hours
SAMA (e.g., ipratropium bromide)	12 hours

Patients should be contacted prior to their visits to remind them to withhold medications as above. Patients should be queried at each visit about their concomitant medications, and visits should be rescheduled if these withhold times are not met. The usual dose of bronchodilators should not be taken the morning of the visit, until after spirometry is performed and prior to dosing (if applicable) with the study medication. Albuterol (salbutamol) 2 puffs, should be dosed prior to study drug both for in-clinic and at-home dosing.

Visits should occur at the same time of day as on Day 1 ( $\pm 2$  hours).

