**Efficacy/PD Measure Visit Windows**

Measure	Mapped Visit (Week)	Target Day	Study Day Window
Spirometry assessments	1 – 1 hour post dose	1	1
	1 – 2 hours post dose	1	1
	3	15	2-22
	5	29	23 to 36
	7	43	37 to 50
	9	57	51 to 71
	9 – 1 hour post dose	57	51 to 71
	9 – 2 hours post dose	57	51 to 71
	13	85	72 to 88
	14	92	89 to 99
CAT and SGRQ	5	29	2 to 43
	9	57	44 to 74
	14	92	75 to 99
EXACT	2	8	2-8
	3-14	15-99	(Week-1)*7-5 to (Week-1)*7+1
Sputum mucins	5	29	23 to 36

Measure	Mapped Visit (Week)	Target Day	Study Day Window
	7	43	37 to 64
	13	85	65 to 88
	14	92	89 to 99
Plethysmography assessments,	14	92	75 to 99

Data collected under visit labels containing Weeks 18, 24, Days 120 or 162 will not be mapped to analysis week.

Visits after Week 14 are part of the post-treatment assessment period. The efficacy and PD data during the post-treatment period will be summarized using the visit labels provided in the data.

Other data will be summarized using the visit labels provided in the data. Multiple results with the same visit label will be averaged. Results with visit labels as “Unscheduled” will not be included in the by-visit summary tables and figures, but will be included in determining baseline, and in the laboratory abnormality summaries and shift analyses.

All data will be presented in data listings.

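### Within an analysis window, an unscheduled reading closer to the target day replaces a protocol-compliant scheduled FEV1, CAT, SGRQ or sputum value, because the SAP gives scheduled visits no priority

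*Combined protocol and SAP*

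**What the plan says.** Under Analytical visits in SAP 3.1.1, "Efficacy/PD data including spirometry, CAT, SGRQ, sputum mucins, ENaC mRNA, inflammatory biomarkers, during the treatment period will be mapped to analysis visit". Unscheduled visits enter on two conditions, closeness to the last dose and position inside a window: "The unscheduled visits will also be included if they are collected within 14 days after the last dose of Study Drug". The choice among competing values is then by distance alone: "the visit nearest the scheduled date will be used unless 2 visits are equally near". Continuous values at equal distance are averaged. Neither the reason for a visit nor its scheduled status plays a part.

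A later paragraph of the same section says that results labelled as unscheduled "will not be included in the by-visit summary tables and figures, but will be included in determining baseline". That paragraph concerns other data, which are summarised by visit label, and it does not reach spirometry or the questionnaires.

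Protocol 3.4 foresees extra visits: "Patients may be required to attend additional visits for monitoring of AEs or abnormal investigation results". Protocol 6.1.3 asks for bronchodilator withholding before each visit after Screening, and "visits should be rescheduled if these withhold times are not met". It also asks that visits keep to the Day 1 clock time within 2 hours.

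**The concern.** A scheduled visit takes place because the calendar says so. An additional visit, on the protocol's stated reason, takes place because something happened to the patient. If the second kind can displace the first, the value representing a study week is partly chosen by the patient's condition, and a valid planned reading is thrown away. If adverse events differ by arm, the effect on the means can differ by arm. The direction is not fixed: acute illness would lower FEV1, and a recent rescue bronchodilator would raise it.

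The SAP also does not make the withholding and time-of-day conditions a requirement for using a value, so nothing in the derivation prevents a non-standardised reading from winning. The measures exposed include FEV1, the primary endpoint. The E-RS diary is not exposed in this way, since its daily scores are averaged within each week.

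**Working it through.** **The plan's own FEV1 figure, as background.** With 116 pooled active and 58 pooled placebo patients, a difference of 100 mL and an SD of 220 mL, SE = 220 × √(1/116 + 1/58) = 35.4 mL. Then 100/35.4 = 2.83, and power = Φ(2.83 − 1.96) ≈ 0.81, which agrees with the stated 80% or more. The present point does not depend on this figure; the 100 mL serves only as a yardstick.

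**When replacement occurs.** Let T be the target day, s the day of the scheduled visit and u the day of the unscheduled one. Under the SAP rule, u replaces s if |u − T| < |s − T|, and the two are averaged if the distances are equal. Targets and analysis windows come from the SAP window table, and permitted visit days from protocol Appendix A. The table takes the scheduled visit on its latest permitted day.

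| Week | Target | Permitted visit days | Analysis window | Latest permitted day | Unscheduled days that replace it | Day averaged with it |
|---|---|---|---|---|---|---|
| 3 | 15 | 13–17 | 2–22 | 17 | 14–16 | 13 |
| 5 | 29 | 26–32 | 23–36 | 32 | 27–31 | 26 |
| 7 | 43 | 40–46 | 37–50 | 46 | 41–45 | 40 |
| 9 | 57 | 54–60 | 51–71 | 60 | 55–59 | 54 |
| 13 | 85 | 83–87 | 72–88 | 87 | 84–86 | 83 |
| 14 | 92 | 87–97 | 89–99 | 97 | 89–96 | none (Day 87 is outside the window) |

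For Week 9, |56 − 57| = 1 is less than |60 − 57| = 3, so Day 56 is kept and the compliant Day 60 value is dropped. A scheduled visit exactly on its target day has distance 0 and cannot be replaced.

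**When an unscheduled value stands in.** If the scheduled visit is missing, any reading in the window becomes the week's value. Days inside the analysis window but outside the permitted visit days number 16 + 7 + 7 + 14 + 12 + 2 = 58, out of 21 + 14 + 14 + 21 + 17 + 11 = 98.

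**Size.** The documents give neither the number of unscheduled spirometries nor the deficit to expect at one, so both are assumptions. Take one substituted value lying d mL below the value it displaces, in a group of n. The visit mean shifts by d/n. The primary time point averages Weeks 13 and 14, so its group mean shifts by d/(2n) if one week is affected and the other is available, and by d/n if the affected week is the only one (SAP, primary time point definition).

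SAP 3.3 reports 10 patients completing Week 14. With the placebo groups pooled (protocol 10.6), the 2:2:1:1 allocation gives three groups of equal expected size, so n is about 10/3, that is 3 or 4. The actual split is not given.

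| Assumed d (mL) | Visit mean, n = 4 | Visit mean, n = 3 | Primary time point, other week available (n = 4 to 3) |
|---|---|---|---|
| 100 | 25 | 33 | 12.5 to 17 |
| 200 | 50 | 67 | 25 to 33 |
| 400 | 100 | 133 | 50 to 67 |

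At an early visit with n near 60/3 = 20, a 200 mL deficit moves the mean by 200/20 = 10 mL.

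**The case against.** The strongest defence is that the rule is deliberate and stated in advance. The SAP says that its windows are not meant to mirror the visit schedule, but to bring together readings near a study week so that they reflect how the patient was at that time. A reading taken while unwell arguably belongs there. That supports keeping unscheduled values. It does not support discarding a valid scheduled one, because except on a tie the rule selects one reading rather than combining them.

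Several stronger readings are tempting, and the documents do not support them:

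- A reader might infer that FEV1 at an extra visit is measured because the patient is unwell. Protocol 3.4 names no spirometry, questionnaire or sputum collection at such visits, and no other section prescribes them there. How often replacement arises is unknown and may be never.
- A reader might infer that extra visits are exempt from standardisation. Protocol 6.1.3 addresses withholding to each visit after Screening and does not limit the time-of-day request to scheduled visits. The gap is only that the SAP does not check compliance before using a value.
- A reader might see an inconsistency with the handling of laboratory data. Those data are summarised by visit label, and an unscheduled label has no row of its own; efficacy data are mapped by day. The two methods differ for a reason.
- A reader might infer that one stray reading becomes the primary result. That needs the other week to be missing as well; otherwise it is averaged with that week's value.

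It also stands that all data are listed, so a substitution can be traced, and that FEV1 falls above 20% are tabulated separately (SAP 3.3.1). Neither tells the reader of a by-visit table that a scheduled value was set aside.

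**Conclusion.** The concern holds as a defect in the selection rule. An unscheduled value strictly nearer the target day displaces a compliant scheduled one, and a tie is averaged. The protocol's stated reason for extra visits means that this can depend on the patient's condition.

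Its reach is limited. SAP 3.3 makes every efficacy analysis descriptive and drops the protocol's model, so no test or error rate is affected. What can move is a summary mean: 50 to 67 mL at a visit with 4 or 3 patients per group, and 25 to 33 mL at the primary time point when its other week is available. The planned effect was 100 mL. These figures assume one substitution, a 200 mL deficit absent from the displaced reading, and about equal group sizes. A scheduled reading a few days away that shared part of the deficit would make the shift smaller. Means of 3 or 4 patients are weak evidence under any rule, but they are what the SAP will report, and the correction is nearly free.

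**What to change.** In SAP 3.1.1, state that within a window the scheduled or Early Termination visit is used when one exists. The nearest-to-target and tie rules then apply only among such visits, or among unscheduled visits when the window holds no scheduled one. A visit rescheduled under protocol 6.1.3 should count as the scheduled visit. Keep an unscheduled value as a stand-in when it is the only value in the window, and flag it in the listings and in table footnotes.

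A stricter rule that drops an only-available unscheduled value unless withholding was documented is not recommended. It could selectively remove unwell patients who needed a bronchodilator, and so create informative missingness.

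The cost is one sentence, one sort key in the derivation program and a flag. An occasional retained value will lie further from its target day than the one it beats. No visit value is lost, and no sample size or power figure changes.

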**Efficacy/PD Measure Visit Windows**

Measure	Mapped Visit (Week)	Target Day	Study Day Window
Spirometry assessments	1 – 1 hour post dose	1	1
	1 – 2 hours post dose	1	1
	3	15	2-22
	5	29	23 to 36
	7	43	37 to 50
	9	57	51 to 71
	9 – 1 hour post dose	57	51 to 71
	9 – 2 hours post dose	57	51 to 71
	13	85	72 to 88
	14	92	89 to 99
CAT and SGRQ	5	29	2 to 43
	9	57	44 to 74
	14	92	75 to 99
EXACT	2	8	2-8
	3-14	15-99	(Week-1)*7-5 to (Week-1)*7+1
Sputum mucins	5	29	23 to 36

Measure	Mapped Visit (Week)	Target Day	Study Day Window
	7	43	37 to 64
	13	85	65 to 88
	14	92	89 to 99
Plethysmography assessments,	14	92	75 to 99

Data collected under visit labels containing Weeks 18, 24, Days 120 or 162 will not be mapped to analysis week.

Visits after Week 14 are part of the post-treatment assessment period. The efficacy and PD data during the post-treatment period will be summarized using the visit labels provided in the data.

Other data will be summarized using the visit labels provided in the data. Multiple results with the same visit label will be averaged. Results with visit labels as “Unscheduled” will not be included in the by-visit summary tables and figures, but will be included in determining baseline, and in the laboratory abnormality summaries and shift analyses.

All data will be presented in data listings.

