## Appendix A. Schedule of Procedures (Continued)

	Screen	Run-in Period	Treatment Period (13 Weeks)							Post-Treatment Period (10 Weeks)+		
Study Week/Day	S-28 to S-7	Day -7	W1 D1	W3 D15	W5 D29	W7 D43	W9 D57	W13 D85	W14 D92 (and Early Term)	W15 D99	W18 D120	W24 D162
Visit Window (Days)	NA	± 1	NA	± 2	± 3	± 3	± 3	± 2	± 5	± 5	± 5	± 5
Scheduled Visit Number	1	2	3	4	5	6	7	8	9	9a	10	11
Diffusing Capacity	X											
Administer SGRQ and CAT questionnaires	X		X a		X a		X a		X			X a
Inflammatory biomarkers 			X a						X			X
Dispense electronic diary and instruct in its use		X										
Collect electronic diary									X			
ECG (12-Lead) in Triplicate	X		X d	X a	X a		X d	X a	X			X
Study Drug (ION-827359 or placebo) Administration 			X	X	X	X	X	X				
Dispense Study Drug for home administration			X 			X 						
Educate on use of nebulizer and dispense			X									
Review use of nebulizer		X		X	X	X	X					
Collect nebulizer								X				

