### **Time (time is in reference to Study Drug (ION-827359 or placebo) administration):**

a Pre-dose

b Pre- and 20-30 minutes post-albuterol dose

c Pre-dose, and 2 hour

d Pre-dose, 1, and 2 hour

e For the subset of patients with full PK sampling; Pre-dose, 0.5, 1, 1.5, 2, 3, 4, 6, 8,12, 24 hours post-inhalation (window of  $\pm$  10% of the timepoint in minutes)

f In the morning, prior to study visit

g Perform spirometry (pre-Study Drug) pre and 20-30 minutes post albuterol dose (2 puffs) and then perform spirometry 1 and 2 hours post-Study Drug dosing.

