#### **3.4.4 Vital Signs, Weight, and BMI**

Vital signs will include heart rate, respiratory rate, body temperature, systolic and diastolic blood pressure and pulse pressure. Summary tables will be created to present the descriptive statistics for vital sign values, weight, and BMI as well as the change and percent change from baseline at each study visits.

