#### **3.4.6 12-Lead Electrocardiograms (ECG)**

The ECG data will include heart rate, RR interval, PR interval, QRS Duration, QT interval, QTcF, QTcB, and overall interpretation.

For the continuous variables above, descriptive statistics of the results at each study visit, as well as the changes and percent changes from baseline to each study visit, will be summarized by treatment group. The average of triplicates will be used in the summary. For the categorical responses to overall interpretation, the counts and percentages will be tabulated by treatment group. The worst case result of triplicates will be used in the summary.

In addition to the descriptive summary, a shift analysis from baseline to the worst (highest) post-baseline QTcF and QTcB by treatment group will be conducted. The categories for the shift analysis will be:  $\leq 450$  msec,  $> 450$  msec to  $\leq 480$  msec,  $> 480$  msec to  $\leq 500$  msec, and  $> 500$  msec. The average of triplicates will be used to categorize the data.

The number and percent of patients experiencing an increase from baseline in QTcF and QTcB of greater than 30 msec or 60 msec at any time post-baseline will be summarized by treatment group. The average of triplicates will be used to determine the increase.

Only data collected from the central reader and provided by ERT will be included in the summary table. The local ECG data will only be listed if collected.

The ECG data will be presented in a subject listing.

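### SAP 3.1.1 averages results sharing a visit label with no time-point qualifier, so unless the labels carry the time point, by-visit ECG and vital-sign means blend pre-dose with post-dose readings

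*Combined protocol and SAP*

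**What the plan says.** SAP 3.1.1 maps efficacy and PD data to analysis windows. Everything else follows two sentences placed after the window table: "Other data will be summarized using the visit labels provided in the data", and "Multiple results with the same visit label will be averaged". Neither mentions a time point, and the SAP does not define what a supplied label contains.

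Protocol Appendix A schedules several readings on some dosing days:

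- The row "ECG (12-Lead) in Triplicate" carries footnote d on Day 1 and Day 57: "Pre-dose, 1, and 2 hour". The other dosing-day ECGs (Days 15, 29 and 85) are pre-dose only.
- The vital-signs row carries footnote c on Day 1 and Day 85: "Pre-dose, and 2 hour". The other dosing days are pre-dose only. No 1-hour vital signs are scheduled.

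SAP 3.4.6 plans, for the continuous ECG variables, "descriptive statistics of the results at each study visit, as well as the changes and percent changes from baseline to each study visit". SAP 3.4.4 does the same for vital-sign values, "weight, and BMI as well as the change and percent change from baseline at each study visits". Neither section names a time point. Spirometry differs: the window table gives it separate post-dose rows, for example "9 – 1 hour post dose". SAP 3.5.1 likewise tabulates PK concentrations by scheduled time point.

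**The concern.** Appendix A gives each dosing day a single visit number (Day 1 is Visit 3, Day 57 Visit 7, Day 85 Visit 8). If the data carry only that visit label, the rule reduces the day's pre-dose and post-dose readings to one mean. On Day 1 that puts the baseline reading into its own follow-up value and pulls the displayed change towards zero. The same factor shrinks any difference between active and placebo in acute change.

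These are the only scheduled ECGs and vital signs within hours of inhalation, and abnormal findings in both are named safety endpoints (SAP 1.3.3). Day 1 matters most. Treatment stopped with 59 patients dosed and 10 through Week 14 (SAP 3.3), so Day 1 is the one post-dose visit that every dosed patient reached.

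**Working it through.** The plan states no figure on this point, so there is none to reproduce. The check is the arithmetic of the averaging rule, on the assumption that the label omits the time point.

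**Inputs**

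- ECG on Days 1 and 57: three time points (Appendix A, footnote d).
- Vital signs on Days 1 and 85: two time points (Appendix A, footnote c).
- Baseline: the last triplicate before first dose for ECG, and the last non-missing value before first dose for vital signs (SAP 3.1.1). Where the Day 1 pre-dose reading was taken it is the baseline, so its change is 0.

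**Day 1 ECG.** Let d1 and d2 be the true changes at 1 and 2 hours, in the same direction.

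Displayed change = (0 + d1 + d2) / 3

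Take a peak effect of 10 units, chosen only for illustration:

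| Pattern | Calculation | Displayed | Loss against the peak |
|---|---|---|---|
| Equal at 1 h and 2 h | (0 + 10 + 10)/3 | 6.7 | one third |
| One reading half the other | (0 + 10 + 5)/3 | 5.0 | one half |
| At one time point only | (0 + 10 + 0)/3 | 3.3 | two thirds |

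**Day 1 vital signs.** Displayed change = (0 + d2)/2. A 10-unit change at 2 hours appears as (0 + 10)/2 = 5.0, a loss of one half.

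**Days 57 and 85.** Let p be the change from baseline already present before that day's dose, and a the acute increment over it.

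- ECG, Day 57: (p + (p + a1) + (p + a2))/3 = p + (a1 + a2)/3
- Vital signs, Day 85: (p + (p + a))/2 = p + a/2

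The term p is kept in full; only the increment is diluted. For example, suppose half of a 10-unit post-dose change was already present before dosing. Day 57 ECG shows (5 + 10 + 10)/3 = 8.3 with equal post-dose readings, and Day 85 vital signs show (5 + 10)/2 = 7.5.

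**What the rule does not touch**

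- SAP 3.4.6 takes the QTcF/QTcB shift to the highest post-baseline value and counts rises above 30 and 60 msec at any post-baseline time, both on triplicate averages. These keep the peak.
- Visits with one scheduled time point, weight and BMI, and the data listings are unchanged.
- SAP 3.4.4 has no worst-value or threshold table for vital signs. SAP 3.4.6 has none for ECG heart rate, RR, PR, QRS or uncorrected QT. For these the by-visit mean is the only planned summary of size.

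**The case against.** The strongest reply is that the merge is not shown to happen. The SAP uses labels as supplied, and a vendor's label may include the time point. The spirometry rows are weak evidence of intent elsewhere, because spirometry is re-mapped to day windows and needs an explicit table, whereas ECG and vital signs keep their own labels. SAP 3.4.6 also treats the triplicate as the unit of analysis, which fits poorly with pooling three triplicates from one day.

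Part of this stands: the dilution is conditional on the labels. But the triplicate rule only yields one value per time point. It does not say how three time points become one by-visit value, and the only text that does is the averaging rule. If the labels do separate the time points, the SAP still leaves that to an undocumented data convention.

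A reader might infer that the plan hides any acute post-dose effect. The documents do not support that: the QTcF/QTcB shift and threshold counts keep the peak, and the listings hold every reading. Nor are all vital-sign results affected, only the Day 1 and Day 85 means.

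Materiality is also limited. The output is descriptive, no decision rule rests on these means, and few patients will have Day 85 post-dose vital signs.

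**Conclusion.** The point holds in conditional form. Followed literally, and if the supplied labels do not carry the time point, SAP 3.1.1 blends pre-dose with post-dose readings in the by-visit means for ECG on Days 1 and 57 and vital signs on Days 1 and 85.

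On Day 1 the displayed acute change falls short of its peak by one third to two thirds for ECG and by one half for vital signs. These sizes assume that the Day 1 pre-dose reading is the baseline and that the two post-dose ECG changes do not have opposite signs. On Days 57 and 85 only the acute increment over that day's pre-dose value is diluted.

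It would go too far to call this an established bias, since the documents neither define the labels nor show a merged table. It is worth correcting because vital signs and the non-QTc ECG measurements have no other planned summary that would show the peak.

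**What to change.** - **SAP 3.1.1:** limit averaging to repeat results at the same visit and the same nominal time point, such as ECG triplicates.
- **SAP 3.4.6:** summarise ECG by visit and nominal time point, with pre-dose, 1-hour and 2-hour rows on Days 1 and 57.
- **SAP 3.4.4:** do the same for vital signs, with pre-dose and 2-hour rows on Days 1 and 85.
- **Both sections:** show post-dose minus same-day pre-dose change at those visits only. No post-dose ECG is scheduled on Day 85 and no post-dose vital signs on Day 57.

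The cost is SAP wording and a few rows. Per parameter, the extra time-point rows are (3 − 1) × 2 = 4 for ECG and (2 − 1) × 2 = 2 for vital signs, plus the same-day change rows. No new data are needed.
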